2.2. Rationale for Selection of Investigational Product

Rituximab is a chimeric mouse/human monoclonal antibody approved as early as 1997 for use in Non-Hodgkin's Lymphoma, Chronic Lymphocytic Leukemia, Rheumatoid Arthritis (RA) in combination with methotrexate in adult patients with moderately-to severely-active RA who have inadequate response to one or more TNF antagonist therapies, Wegener's Granulomatosis and Microscopic Polyangiitis in combination with glucocorticoids. Rituximab targets CD20, a cell surface expressed protein found immature, transitional, mature and memory B cells but is absent on antibody producing plasma cells. While its exact mechanism of action is not fully understood, multiple studies in adults with autoimmune diseases such as Systemic Lupus Erythematosus (SLE) or RA showed that rituximab markedly depletes CD19+HLA-DR+⁵⁷ and memory CD19+CD27+ B cells.⁵⁸ Switched memory B cells (CD27+IgD-) are

relatively spared compared to CD27-IgD+ naïve B cells and CD27+IgD+ unswitched B cells.⁵⁸ Further in RA patients, responders to rituximab therapy showed a significant decrease in CD19+CD27+ memory B cells compared to non-responders indicating that response may be impacted by the subset of B cells affected.⁵⁷ One important consequence of rituximab-induced B cell depletion is that the host B cell repertoire repopulates over the ensuing 3-6 months. This reconstitution process appears to recapitulate B cell ontogeny, where immature B cells undergo negative selection on stromal cells in the bone marrow and emerge with a transitional phenotype into the periphery.⁵⁹ Transitional B cells, characterized by expression of CD38hiCD24hiIgD+CD27-CD10+/-,⁶⁰ require survival signals provided by the cytokines BAFF and APRIL and are key intermediaries in the development of the mature B cell repertoire. Evidence suggests that the transitional B cell population contains B reg and that transitional B cells are subject to mechanisms of self-tolerance in the periphery.

Rituximab has been safely used in pediatric patients

In pediatrics, rituximab is safe when used for multiple indications including B-cell leukemia/lymphoma, relapsing minimal change disease and focal segmental glomerulosclerosis, calcineurin-dependent nephrotic syndrome and progressive IgA nephropathy.⁶¹ Treatment of post-transplant lymphoproliferative disease in solid organ transplant recipients with rituximab appears both promising and safe.⁶² Further, rituximab has been reported in limited numbers of pediatric lung transplant recipients for treatment of PTLT, AMR and capillaritis.^{63,64} Several protocols for hematopoietic stem cell transplant report safely using rituximab as adjunctive therapy to T-cell depleting induction; this is similar to the proposed intervention arm but in a novel population, pediatric lung transplant recipients. The safety of rituximab in pediatric transplantation is underscored by a recent review of 42 pediatric children's hospitals indicating that 30% of pediatric rituximab use is in pediatric transplant recipients.⁶⁵

Rituximab has been used with some efficacy in transplant recipients to remove pre-existing antibodies.

In adult transplantation, trials evaluating rituximab as induction in sensitized kidney recipients, unsensitized kidney (RESTART) and heart recipients (CTOT-11) are ongoing. Induction with rituximab was successfully reported in a double-blind, placebo controlled study of adult kidney transplant recipients in Sweden without an increased incidence of post-transplant infection.⁶³ In pediatric renal transplantation, Chaudhuri and colleagues reported the resolution of post-transplant nephrotic syndrome recurrence (mediated by autoantibody to nephrin proteins) with rituximab.⁶⁴ Additionally, 4 weekly doses of rituximab was successfully used in trials as a treatment in combination with thymoglobulin and steroids for acute kidney rejection with B-cell infiltrates in pediatric recipients.⁶⁵ No increased risk of infection was observed. Furthermore, pediatric and adult kidney recipients who develop early post-transplant anti-HLA antibodies were randomized to receive 2 (adults) or 4 (children) doses of rituximab or placebo to assess for differences in chronic allograft function (CTOT-02). Data from kidney transplantation suggests that at least 2 doses are needed to achieve effective B-cell clearance.^{69,70}

Use in adult pre-transplant desensitization and adult lung transplantation antibody therapy

While isolated B-cell depleting induction (without T-cell directed induction) was found to be inadequate with increased risk of acute T-cell mediated cellular rejection in one study,⁷¹ B-cell depletion with rituximab in multiple adult studies has been shown to improve outcomes when used as part of ABOi desensitization protocols prior to kidney transplantation.^{72,73} Rituximab has been employed successfully in adult lung transplantation for the same indication in case reports.^{74,75} Furthermore, in adult lung transplant recipients found to have DSA and self-antigens (Ka1T and colV) rituximab was used as part of an antibody depleting regimen. Patients who cleared either DSA or self-directed antibodies were less likely to progress to BOS than patients with persistent antibody.^{76,77} However,

only a subset of subjects cleared either DSA or auto-antibodies with the intervention suggesting that prevention of antibody development from the time of transplantation may be a more effective approach to BOS prevention.

Hypothesis and Dosing rationale

Taken together these studies suggest that rituximab can effectively deplete subsets of circulating B-cells and reduce antibody formation without significantly increasing infectious risk. Moreover its successful use in autoimmune disease suggests that, following reconstitution of the B-cell compartment, autoimmunity may not return. We hypothesize that, due to the injury associated with donor death and the transplant procedure, the early post-transplant period is critical for the development of adaptive immunity (both cellular and humoral). Therefore depletion of the B-cell population during this period will reduce or eliminate the development of adaptive humoral responses to donor antigens and exposed cryptic lung self-proteins and add to the reduction in cellular immunity by reducing the pool of B-cells available to serve as APCs.

We considered other potential interventions to affect antibody mediated pathology including intravenous immunoglobulin or bortezomib (which depletes plasma cells); however, rituximab was chosen due to the established safety profile in pediatric transplant patients coupled with the greatest potential biological impact (i.e. prevention of antibody development via depletion of specific B-cell subsets as opposed to strategies directed at antibody removal).

[figure not shown]
Thus our primary hypothesis is that induction with rituximab (in combination with Thymoglobulin) will improve outcomes following pediatric lung transplantation through a decrease in antibody development post-transplant.

The regimen of 375mg/m² was chosen based on manufacturer labeling for current indications, safety profile and historical pediatric experience with rituximab. In light of the information from prior studies using a single dose of rituximab a second dose is scheduled at day 12 post-transplant consistent with the study design of the adult heart transplant study (CTOT-11). We will assess the level of B cell reduction in the first 8 participants using flow cytometry to ensure B cell reduction in this patient population is equivalent to B cell reduction obtained in other studies.

2.3. Preclinical Experience

In the murine model for OAD previously established in the [name] lab, non-complement fixing MHC class I Abs were administered intra-tracheally to wild type mice and complement factor C3 knock out (C3KO) mice. Both groups developed OAD as evidenced by increase in cellular infiltration and fibrosis around the vessels and bronchioles (**Figure 1**).

[figure not shown]
This was associated with development of T-helper (Th)-17 type immune responses to ColV and α 1T and up-regulation of profibrotic cytokines and growth factors. This indicates complement activation is not necessary in the pathogenesis of chronic rejection following lung transplantation.

2.4. Clinical Studies

The funded and ongoing CTOTC-03 trial is a prospective, observational study to evaluate the impact of respiratory viral infections on the development of allo- and autoreactivity in pediatric lung transplant recipients. The team has laboratory results on 36 patients thus far.

While positive class I (3%) or class II (0%) DSA pre-transplant were rare, significant numbers developed class I and class II DSA within 3 months post-transplant (**Figure 2**).

[figure not shown]

Autoantibodies to ColV and α 1T were detectable prior to transplant in 33% and 44% of subjects, respectively. Post-transplant, de novo DSA and autoantibodies to both self-antigens occurred frequently, with α 1T most common. Correlations between antibodies and outcomes have not been assessed to date.

These results indicate both allo- and autoantibodies develop frequently and early following pediatric lung transplantation supporting our contention that induction therapy targeting B cells will be required to prevent and/or eliminate these antibodies.

We analyzed recipient T cells for reactivity to donor antigens (when donor tissue was available) and to ColV and α 1T as putative autoantigens. We observed 9/26 (35%), 2/36 (6%) and 21/36 (58%) of the recipients exhibited significant frequencies of IFN γ producing cells to donor and/or autoantigens (ColV and α 1T) posttransplant, respectively.

To expand upon these techniques to test for IL-17 production (IL-17 has been associated with BOS in recent adult transplant recipients²⁵) with limited available cells from pediatric patients we developed a 2 color IFN γ /IL-17 ELISPOT assay (**Figure 3**).

CTOTC-03 tested for respiratory viral infections as a potential trigger for immune activation. We evaluated prospective serial nasopharyngeal (NP) and bronchoalveolar lavage (BAL) specimens and interrogated by respiratory multiplex PCR (Luminex xTAG) that identifies 17 viruses.

Preliminary epidemiologic data revealed 23 of 31 (74%) of subjects had at least one positive viral specimen. The median time to virus-positive specimens was 65 days post-transplant (range 1-599). Rhino/enterovirus was recovered most frequently (40 episodes) compared to coronavirus (3), hMPV (1), influenza (2), RSV (2), adenovirus (1), parainfluenza (1). Rhino/enterovirus occurred throughout the year but the other viruses were detected in the winter/spring months. Along with previous infectious diseases epidemiology, we have the capacity to monitor for and respond to changes in the rates of infectious episodes in our patient population.

Development of Abs to HLA following Lung Transplant and its impact on the development of BOS:

Since 2006, the Washington University adult lung program and the [name] lab instituted serial analysis for development of Abs to donor mismatched HLA during the post-transplant period. All adult LTxR had negative donor cross-matches. Of 116 patients serially analyzed, 65 developed DSA (56%), with 52 in the first 90 days, again supporting our contention that early intervention will be required to prevent induction. To test the hypothesis that antibodies contribute to late graft injury, the [name] group used IVIG (500 mg/kg x 6 monthly doses) and rituximab (375 mg/m² x 1 dose) for desensitization. Of the 44 patients treated, 27 (61%) cleared the DSA, and 17 (39%) had persistent DSA. An additional 17 patients were treated with IVIG alone and 11 (65%) cleared the DSA. More importantly, patient and graft survival was significantly better in successfully desensitized patients (Figure 4) providing strong correlative evidence that DSA participate in the development of allograft injury.⁷⁸

[figure not shown]

Figure 4: Improved survival following clearance of DSA.

A critical role for Abs to self-Ags in the pathogenesis of BOS:

Among adult LTxR who developed DSA (n=57) and subsequently cleared DSA following Ab directed therapy (n=34), 9 patients nonetheless developed BOS. We detected persistence of Abs to self-Ags, CoIV and κ 1T in most of these individuals, strongly implicating pathogenic roles for Abs to self-Ags. As shown in **Figure 5**, the LTxR who cleared both Abs to HLA and self-Ags demonstrated improved freedom from BOS in comparison to patients that cleared only DSA but not Abs to self-Ags.

[figure not shown]

Figure 5: Increased incidence of BOS in DSA cleared LTx patients following Ab directed treatment when Abs to self-Ags persist

Taken together, these preliminary results strongly support our hypothesis that Abs to self-Ags play a critical role in the pathogenesis of BOS and our proposed study will assess both the impact of intervention and further determine significance and mechanisms of antibodies to self-antigens.

Successful post-transplant desensitization of Abs to self-Ags in adult LTxR:

To determine whether a post-transplant desensitization regimen for DSA with rituximab and IVIG has an impact on the Abs to self-Ags, we analyzed 123 LTxR who developed DSA. Forty-five LTxR had Abs to κ 1T and 31 had Abs to CoIV prior to desensitization. Following treatment 46.7% of the κ 1T+ and 48.4% of the CoIV+ became negative and another 25% demonstrated a significant decrease. This study demonstrates that rituximab-based desensitization of Abs to self-Ags is feasible.

Correlation between antibodies to self-Ags and pro-inflammatory milieu persists with continued Abs to self-Ags even after DSA clears: To determine the mechanisms by which Abs against HLA and self-Ags may contribute to the pathogenesis of BOS, were performed serum cytokine analysis using 25-plex Luminex assay. We analyzed sera from three groups of patients: group I DSA and Abs to self-Ags present (prior to therapy), group II cleared DSA but Abs to self-Ags persisted and group III cleared both DSA and Abs to self-Ags.

Results presented in **Figure 6** demonstrate that group I patients who had both DSA and Abs to self-Ag (n= 23) as well as group II that cleared DSA but persisted Abs to self-Ag (n=9) had high levels of pro-inflammatory cytokines. In contrast, group III cleared DSA and Abs to self-Ags (n=25) and did not develop BOS had decreased levels of pro-inflammatory cytokines (namely IL-1 β (3.2 fold decrease), IL-17 (3.0), and IFN- γ (2.3)) and increased IL-10 (3.7 fold, p<0.01 for all) within 6 months. These results support persistent immune responses to self-Ags can lead to a pro-inflammatory milieu that can facilitate the development of BOS.

Increased frequency of B cell with autoimmune phenotype in BOS:

Data from mouse models and humans with autoimmune diseases suggest an important role for a specific subset of B cells in the pathogenesis of autoimmune diseases⁷⁹⁻⁸¹. These B cells express CD11c, produce autoantibodies and can be induced to proliferate in response to TLR stimuli. To determine whether this subpopulation of B cells is increased in adult LTxR with BOS we determined the frequency of the autoimmune B cells (AIB) with phenotype of CD19+, CD11c+ B220+ in peripheral blood of LTxR with BOS and Abs to self-Ags. Results presented in **Figure 7** demonstrate a five-fold increase in the AIB (9.6 \pm 2.8% of B cells) over normal (1.6 \pm 0.7% of B cells). To determine whether those B cells are present in the lung allografts, BAL cells were characterized. Results demonstrate that the BOS(+) LTxR who had Abs to self-Ag demonstrate a 3.5 fold increase over BOS(-) LTxR (9.3 \pm 2.1% vs. 2.8 \pm 1.2% of B cells, n=6). It is of interest that BOS(+) anti self-Ag(-) LTxR showed similarly low frequency of AIB as in BOS(-) LTxR (data not shown). These results strongly favor our contention that AIB may play a role in immune responses to self-Ags and development of BOS, which will be tested in the mechanistic study.

Circulating B cells in BOS(+) LTxR augment the frequency of self-Ag specific Th17 cells:

To determine the role of B cells to activate self-Ag specific T cells, T cells isolated from BOS(+) self-Ab(+) or BOS(-) self Ab(-) LTxR were cultured with sub-optimal concentrations of α 1T or ColV (100ng/ml) with or without B cells. At the end of 2 weeks, the frequency of Th17 cells was analyzed by ELISPOT.

[figure not shown]

Figure 6: Increased Pro-inflammatory cytokines in LTx patients with persistent DSA and Abs to self-Ags correlated with BOS.

[figure not shown]

Figure 7: Increased frequency of AIB in PBMC and BAL.

[figure not shown]

Figure 8: Frequency of Ag specific Th17 cells increases in the presence of B cells.

Results in **Figure 8** demonstrate that in the presence of B cells there was a significant increase in the frequency of Th17 cells specific for $\kappa\alpha 1T$ and ColV when compared without B cells. BOS(-) self-Ab(-) LTxR or cells from normal volunteers failed to respond.

BOS(+) LTxR with significant increase in pro-inflammatory environment even without Abs to HLA, ColV and $\kappa\alpha 1T$:

Sera from LTxR with BOS but neither DSA nor Abs to self-Ags (ColV, $\kappa\alpha 1T$) were analyzed for serum cytokines using Luminex. LTxR who developed BOS (24%, 12/51) but did not develop Abs to HLA or ColV and $\kappa\alpha 1T$ had elevated levels of IL-17 (8.2), IFN- γ (3.7) and decreased levels of IL-10 (2.9) suggesting that induction of Th17 immune responses may play a role even in the absence of humoral responses to HLA, ColV and $\kappa\alpha 1T$.

3. Study Design

3.1. Description of Study Design

This is a phase 2, prospective, multi-center, double-blind, randomized, placebo-controlled clinical trial in which 50 primary pediatric lung transplant recipients will be randomized (1:1) to receive either induction therapy with anti-CD20 mAb (375 mg/m²) IV or placebo (IV day 0 and day 12 post-transplant) plus standard of care immunosuppression (thymoglobulin induction, tacrolimus or equivalent, MMF or equivalent, and steroids). The study will randomize 50 primary pediatric lung transplant recipients from seven participating centers. Subjects will be screened, consented, and enrolled while on the UNOS waitlist. When the recipient has received the transplant and is deemed hemodynamically stable, randomization will occur.

[figure not shown]

Figure 9: Study Design

3.2. Primary Endpoints

The primary endpoint is the earliest time to any of the following events during the follow-up period:

- Chronic Allograft Dysfunction
- Listed for Retransplant
- Death

3.3. Secondary Endpoints

The following *secondary clinical endpoints* will be assessed:

1. Post-transplant outcomes including:
 - a) Incidence of chronic allograft dysfunction, relisting and death during the follow-up period, which will be a minimum of 12 months post-transplant;
 - b) Incidence of Primary Graft Dysfunction;
 - c) Incidence of Grade A Acute Rejection during the follow up period, which will be a minimum of 12 months post-transplant;
 - d) Incidence of Antibody Mediated Rejection during the follow up period, which will be a minimum of 12 months post-transplant;
 - e) Incidence of tacrolimus variability threshold during the follow up period, which will be a minimum of 12 months post-transplant;
 - f) Percentage of participants meeting tacrolimus variability threshold who complete tacrolimus variability intervention;
 - g) Magnitude of change in standard deviation of tacrolimus levels following intervention.
2. Post-transplant safety outcomes including:
 - a) Incidence and severity of infection episodes; See previous comment in the synopsis above
 - b) Serious adverse events related to rituximab.

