12.3.2 Attribution Definitions

The relationship, or attribution, of an adverse event to the study therapy regimen or study procedure(s) will initially be determined by the site investigator and recorded on the appropriate *AE/SAE eCRF*. Final determination of attribution for safety reporting will be determined by DAIT/NIAID. The relationship of an adverse event to study therapy regimen or procedures will be determined using the descriptors and definitions provided in Table 14.

For additional information and a printable version of the NCI-CTCAE manual, consult the NCI-CTCAE web site: <http://ctep.cancer.gov/reporting/ctc.html>.

Table 14: Attribution of Adverse Events

Code	Descriptor	Relationship (to primary investigational product and/or other concurrent mandated study therapy or study procedure)
UNRELATED CATEGORY		
1	Unrelated	The adverse event is clearly not related: there is insufficient evidence to suggest a causal relationship.
RELATED CATEGORIES		
2	Possible	The adverse event has a reasonable possibility to be related; there is evidence to suggest a causal relationship.
3	Definite	The adverse event is clearly related.

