For safety outcomes, we will analyze each type of infection separately (bacterial, fungal, or viral, including RVI, CMV, and EBV), as well as for all types of infections combined. We will first determine the incidence of bacterial, fungal and viral infections in the rituximab and control groups. 'Incidence rate' will be the number of infections per patient-month, and we will focus on the estimates and associated 90% confidence intervals for the ratio of such rates (RR), where $RR > 1.0$ indicates greater infection rates for rituximab. Of course, infection events are biologically related within patient, thus, relative to perfect independence of events, greater proportions of patients will experience more episodes of the same type of infection and greater proportions of patients will experience no episodes. Accordingly, a Poisson regression models offset for months of follow-up and adjusted for overdispersion will be used to compare groups on the rate of each type of infection and any infection.

Serious adverse events related to rituximab will be reported by their incidence rate per patient and per infusion with 90% confidence intervals. Adverse events will be summarized by treatment group, with 90% confidence intervals.

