The severity of infection episodes will be determined by reconciling all infections, as defined above, against those infections which qualified for adverse event (AE) reporting. Since the protocol restricts AE reporting to only those events which meet NCI-CTCAE grading criteria of Grade 3 or higher, any infections not reported as an AE will be assigned a severity of Grade ‘<3’ (effectively combining Grades 1 and 2); all other infections will utilize the assigned CTCAE severity grade of the corresponding AE. The proportion of subjects within each severity grade will be reported by treatment group with a corresponding 90% confidence interval; treatment groups will be compared using a Chi-square or Fisher’s Exact test. This presentation will be repeated for the number of events divided by person time, where time is the same across severity groups.

Variable: Serious adverse events (SAEs) related to rituximab

Analysis: For all SAEs, assessment of the relationship to rituximab will be made by the DAIT medical monitor. The proportion of subjects with SAEs determined to be related to rituximab will be reported by treatment group with 90% confidence intervals, and treatment groups will be compared using Chi-square or Fisher’s Exact test.

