8.3. Deaths and Serious Adverse Events

Serious adverse events (SAEs) will be summarized in a manner consistent with that described in Section 8.2, and when appropriate SAEs may be summarized in the same table as all AEs.

Separate listings detailing each death, including time to and cause of death, will also be created.

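### The only planned between-arm test of SAEs is limited to those judged related to rituximab; all-cause SAEs have no between-arm estimate, and the SAP drops the protocol's 90% intervals

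*Protocol*

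**What the plan says.** The SAE safety outcome is worded "Serious adverse events related to rituximab" (Protocol 3.3, item 2b; the synopses and Protocol 13.2 agree).

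**Attribution.** Protocol 12.3.2 has the site investigator attribute first, and then "Final determination of attribution for safety reporting will be determined by DAIT/NIAID". SAP 7.3.2 says: "For all SAEs, assessment of the relationship to rituximab will be made by the DAIT medical monitor".

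**Analysis of related SAEs.** Protocol 13.4.4: "Serious adverse events related to rituximab will be reported by their incidence rate per patient and per infusion with 90% confidence intervals". SAP 7.3.2: "The proportion of subjects with SAEs determined to be related to rituximab will be reported by treatment group with 90% confidence intervals". The same sentence of the SAP adds a test between the arms, either Chi-square or Fisher.

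**Analysis of SAEs of any cause.** Protocol 12.5.1 requires sites to report every SAE whatever its relationship to treatment. Protocol 13.4.4: "Adverse events will be summarized by treatment group, with 90% confidence intervals". SAP 8.3: "Serious adverse events (SAEs) will be summarized in a manner consistent with that described in Section 8.2". SAP 8.2 lists numbers of events and numbers and percentages of subjects. It names no interval, effect estimate or test.

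**Sample.** SAP 7.3.2 uses the SAP's safety sample. That is every consented subject with a pre-transplant blood draw, with randomised subjects grouped by treatment received. Protocol 13.4.1 instead defines the safety sample as the ITT sample: randomised subjects who received at least part of the first infusion.

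**The concern.** Secondary objective 2 is the safety and tolerability of rituximab. In a placebo-controlled trial, the direct evidence on whether the drug causes SAEs is the difference in all SAEs between arms. The plan tests a difference only after each event has been sorted by a case-by-case opinion.

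That sorting is hard in this population. All children also receive thymoglobulin, tacrolimus, MMF and steroids. Protocol Table 14 places an SAE in the unrelated category when evidence for a causal link is insufficient. A single cytopenia or admission can easily fall there. The protocol recognises the difficulty: its expedited-reporting section (12.5.2.2, Category 1, item 3) treats an aggregate excess over a control group as evidence of causation for events that are common in the study population. The SAP plans no such contrast for SAEs.

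Cytopenias make the point sharper. Under Protocol 12.3.1, from the first infusion to six weeks after the last, they are collected only if serious. In that window the SAE data are the only adverse-event record of them.

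At stake is a safety report that gives a p-value for attributed SAEs and leaves readers to work out the all-cause contrast from a table.

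**Working it through.** The documents give no SAE rate, attribution rate or power for this endpoint, so there is no planned figure to reproduce. The first step sets the texts side by side. The others are illustrations on assumed rates.

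**1. What is compared, and how**

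| Outcome | Attribution filter | By-arm 90% CI | Between-arm analysis |
|---|---|---|---|
| Related SAEs (SAP 7.3.2) | Yes | Yes | Chi-square or Fisher test |
| All SAEs (SAP 8.2, 8.3) | No | Not named (Protocol 13.4.4 promises it for adverse events) | None |
| Infection rate (SAP 7.3.2) | No | Not named | Overdispersed Poisson rate ratio, 90% CI |
| Infection severity (SAP 7.3.2) | No | Yes | Chi-square or Fisher test |
| Death (SAP 7.2.2, 7.3.1) | No | Yes | Own Cox model, 90% CI |

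The gap is in the second row.

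**2. Dilution by even-handed attribution**

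Let p0 be the background SAE risk, e the true excess on rituximab, s the share of drug-caused SAEs recognised as related, and f the share of background SAEs wrongly called related, equal in both arms. In a simple additive model:

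- placebo: p0 × f
- rituximab: p0 × f + e × s
- visible difference: e × s

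With assumed p0 = 50% and e = 25 points:

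| s | Related, f = 5% (placebo v rituximab) | Related, f = 20% (placebo v rituximab) | Visible difference | True excess |
|---|---|---|---|---|
| 30% | 2.5% v 10% | 10% v 17.5% | 7.5 points | 25 points |
| 60% | 2.5% v 17.5% | 10% v 25% | 15 points | 25 points |
| 90% | 2.5% v 25% | 10% v 32.5% | 22.5 points | 25 points |

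The visible excess shrinks in proportion to s, whatever f is.

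**3. Precision of an all-SAE rate ratio**

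Inputs: 25 per arm (Protocol 3.1: 50 randomised 1:1). Assumed: one year of follow-up, m = 1 or 2 SAEs per child-year on placebo, true rate ratio 1.5, gamma frailty with shape 1 (so the count variance is m + m²).

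Var(log RR) ≈ (1/m + 1)/25 + (1/(1.5m) + 1)/25

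- m = 1: 2/25 + 1.667/25 = 0.147, SE 0.383. z = 0.405/0.383 = 1.06. Power at two-sided 0.10 ≈ P(Z > 1.645 − 1.06) = 28%. Expected 90% CI: 1.5 divided and multiplied by exp(1.645 × 0.383) = 1.88, about 0.80 to 2.82.
- m = 2: 1.5/25 + 1.333/25 = 0.113, SE 0.337. z = 0.405/0.337 = 1.20. Power ≈ 33%. Expected 90% CI: factor 1.74, about 0.86 to 2.61.

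**4. The planned Fisher test under the same assumptions (simulation)**

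| Drug-caused / background SAEs called related | Planned test, power | All-SAE rate ratio, power |
|---|---|---|
| 10% / 2% | 1–11% | 28–33% |
| 20% / 2% | 9–37% | 30–33% |
| 30% / 5% | 23–44% | 29–35% |

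Ranges cover m = 1 to 2. The planned test moves widely with the assumed attribution shares; the all-SAE estimate barely moves.

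**5. The yes/no proportion alone is not enough**

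For all-cause SAEs as a proportion at 25 per arm, the Wald 90% half-width is 1.645 × √(p1(1−p1)/25 + p2(1−p2)/25). An assumed 50% v 70% gives 22 points, with 33% Fisher power at two-sided 0.10. An assumed 90% v 96% gives 12 points and 5% power. If nearly every child has an SAE, only the rate is informative.

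**The case against.** The strongest reply has four parts.

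- **Most safety outcomes carry no filter.** Infections and death are compared without attribution, and the stopping rules in Protocol 12.8.2 count events regardless of cause. This stands. A reader might infer that the trial's whole safety conclusion rests on opinion; the documents do not support that.
- **All-cause intervals are planned.** Protocol 13.4.4 promises by-arm 90% CIs for adverse events, and SAEs are a subset. This stands for the protocol. SAP 8.2 and 8.3 do not carry the intervals over, and neither document names a between-arm SAE contrast, although Protocol 13.4 sets comparative 90% CIs as the focus for each endpoint.
- **Attribution is legitimate and can help.** Blinded attribution applied alike to both arms keeps a valid, if diluted, randomised comparison. Generous and accurate attribution removes background noise and can beat the all-cause analysis (44% v 35% at the top of the 30%/5% row). So it would be wrong to say that the filter can only distort, or that it sets randomisation aside.
- **The monitor is not shown to be unblinded.** A reader might infer from the unblinded IND safety reports (Protocol 3.5) that the monitor knows the arm, so that placebo subjects could never have a related SAE. Those reports go to the FDA, DSMB and IRBs, and health-authority reporting follows the sponsor's assessment (12.5.2). Emergency unblinding, in which the monitor takes part (3.5.1, 8.7.3), is confined to exceptional cases. What remains is a silence: blinding is stated for participants and site clinical staff, and the monitor is not mentioned.

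Related SAEs are also a disclosed, prespecified choice in a 50-child phase 2 trial. That argues for adding an analysis and against replacing one.

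**Conclusion.** The point holds for the SAE result. The only between-arm SAE test is on attributed events; all-cause SAEs have no planned contrast and lose their protocol intervals in the SAP. Even well-conducted attribution shrinks a true excess by the factor s, to 7.5 points out of 25 at s = 30%, and the monitor's blinding is unstated.

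This is an inexpensive improvement and does not touch the primary result. The SAE rates, rate ratio, frailty and attribution shares above are all assumptions. Under them an all-cause rate ratio has about 30% power for a true ratio of 1.5, with a 90% CI that would typically include 1. Its value is that it does not depend on attribution, not that it would settle the question.

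The SAP's safety sample is grouped by treatment received and includes subjects never randomised. Adding all-cause SAEs there would not give a randomised contrast, so the sample has to be named as well.

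**What to change.** In SAP 7.3.2, add all treatment-emergent SAEs regardless of attribution, using the definition of treatment-emergent already in SAP 8.2. Analyse them in the ITT sample as randomised, which Protocol 13.4.1 also makes the safety sample. Report:

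- subjects with at least one SAE: risk difference and risk ratio with 90% CI;
- SAEs per person-time: rate ratio with 90% CI from the overdispersed Poisson model already specified for infections.

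Then:

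- restore the by-arm 90% CIs of Protocol 13.4.4 in the SAP 8.2 and 8.3 tables;
- keep related SAEs as a supportive summary by arm;
- state in SAP 7.3.2 and Protocol 12.3.2 that attribution is made blind to arm, and flag any SAE attributed after that subject was unblinded;
- align Protocol 3.3 item 2b and 13.4.4.

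Cost: wording and one more run of an existing model on data already collected. The downside is background noise and a wide interval, which is why the related-SAE summary should stay alongside.
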